A sample of 60 patients scheduled for HSCT in the treatment of MM will be recruited in the weeks to months prior to their hospitalization. Light therapy incorporating ambient systematic programmed light illumination (sPI) will be used in patient hospital rooms (during scheduled transplant) to control cancer-related fatigue (CRF). The FDA has certified that light therapy, like that used in this study, is a low-risk intervention. After initial assessment of CRF, depression, and sleep quality/quantity (baseline assessments), participants will be randomized to one of two treatment conditions: one with an active intervention, and one with a non-active comparison. During inpatient hospitalization, the active intervention will consist of the following regimen: high intensity bright-white light (1300 lux at the eyes) during morning hours (7AM to 10AM). The non-active comparison condition will receive half the intensity dim-white light of the active group (i.e., 90 lux at the eyes) during 7AM-10AM. These differences in lux intensity are not easily discernable. Following baseline, assessment of fatigue, sleep activity, depression, circadian rhythms, and quality of life will continue through the course of hospitalization (14-21 days of treatment, to determine immediate impact of sPI), then repeat at one month and threemonths post-discharge follow-ups (to determine lasting effects). Outcomes will be assessed through standardized scales (e.g., FACIT-Fatigue Scale) and objective measures (e.g., actigraphy, daysimeter for light monitoring, melatonin from urine collection, blood inflammatory markers, all explained below). This trial will: 1) be the first randomized clinical trial (RCT) to investigate the effects of sPI to prevent CRF and other biopsychosocial side effects of transplant; 2) focus on a distinct, relatively homogenous patient population (MM-HSCT patients) with high prevalence of CRF; and 3) explore possible circadian rhythm mediation via melatonin analysis and blood analysis. This investigation will have major public health relevance as it will determine if an inexpensive and low patient burden intervention (sPI) is able to control fatigue associated with medical illnesses and related problems.

1) Objectives

Specific Aims:

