- **Aim 1: Determine if sPI results in significant prevention/reduction of the development of CRF, depression, sleep problems, circadian rhythm disruption and diminished quality of life compared to the comparison light condition.** Hypothesis 1a: HSCT patients exposed to sPI will report less CRF (measured by FACIT-Fatigue Scale), less depressive symptoms (measured by the CES-D/BDI-II), better sleep (measured subjectively by the Pittsburgh Sleep Quality Index, FACIT Fatigue Scale and objectively by actigraphy), and more synchronized activity circadian rhythms (measured by actigraphy) during the course of HSCT hospitalization compared to those patients in the low light comparison condition. Hypothesis 1b: HSCT patients receiving sPI will report positive effects on CRF, depression, sleep, and circadian rhythm disruption at one month and three-

	Protocol Name:	Systematic Programmed Illumination of Hospital Rooms to Prevent/Reduce Cancer-Related Fatigue during Autologous Stem Cell Transplantation for Multiple Myeloma
	Principal Investigator:	[name]; [contact]
	Primary Contact Name/Contact Info:	[name], [contact], [contact]
	Date Revised:	8/15/2019
	Study Number:	IF# 2517160 HS# 15-00777 GCO#: 15-2009

months after discharge and completion of the sPI intervention than those in the comparison condition.

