of Life), hierarchical random effects linear mixed models will be employed for Aims 1 and 2 using MIXED with repeated measures. Besides time (linear and possibly quadratic trends to allow for possible nonlinear trends), any covariates identified in the preliminary analyses and intervention group will be assessed in a fixed effects model. Each model will also include a random intercept. Post-hoc comparisons will be Tukey-adjusted. Since there are multiple secondary outcomes, the p-values will be Sidak adjusted for correlated multiple comparisons. Any variations in length of hospital stay (i.e., length of intervention) will be used as a covariate in all analyses. This is highly unexpected since 90% of ASCT patients are hospitalized for 14 days. In the Analysis of Aim 2, we will establish that the treatment is a significant predictor of the primary outcome (CRF) as well as the hypothesized mediators. Next, we will first examine the role of each of the mediators of the effects of sPI on CRF by introducing each individually into the equation which contains the time variable, the treatment main effect, and the time by treatment interaction. Each mediator which is a significant predictor of CRF in this equation will then be combined with any other significant mediating predictor of CRF into a single equation. We predict the introduction of each significant mediator will result in the decrease in the significance of the time by treatment interaction effect on CRF. However, the more important test of the mediating role by any variable will depend on the statistical significance of the indirect path from treatment to mediator and from mediator to the outcome. Following procedures suggested by Shrout and Bolger (2002), 1000 bootstrap samples will be employed to determine the significance of each indirect path.⁵⁰ **Power:** It is difficult to discuss power for **Aim 1** and **Aim 2** since there is no directly relevant past research. As a consequence, one of the goals of this project is to obtain estimates of the effect sizes that will eventuate from our proposed analyses. Although unknown at the moment, these effect sizes can guide decisions regarding sample sizes for a larger scale grant. In the interim, there are three lines of research that may provide some guidance. The first involves the work of [name], who investigated the effects of light treatment on fatigue experienced by women undergoing chemotherapy for breast cancer.⁹ Using her results, we calculated power for a repeated measures design with an autoregressive lag 1 structure and autocorrelations ranging from 0.40 to 0.60. With alpha equal to 0.05 and a sample size of 30 patients per group, power ranged between 0.96 and 0.98. We followed a similar approach using [name]'s results but focusing only on MM survivors of ASCT.¹⁰ In this case, power was 0.99 for autocorrelations ranging between 0.40 and 0.60. However, the latter results must be treated cautiously because these calculations were based on a very small sample (N = 17 survivors). Using the same small sample, our repeated measures analysis of depression indicated that the time by treatment condition interaction was marginally significant (p = 0.0568). The F-ratio for this interaction yielded an eta coefficient of 0.48 which would be considered moderately strong following Cohen's criteria.⁴⁹ We hypothesize that the interaction effect would have been significant had the sample size been larger as is being proposed in this study (N = 60). Because of the very small survivors sample and the variability of our indicator of circadian activity rhythms (the f-statistic), the Mixed program did not converge and it was not possible to obtain a power estimate for this outcome. The third line of research that is germane to power in the proposed pilot study was conducted by Sim and Lewis who applied the UCL approach and found that a pilot sample of n => 55 would minimize the overall sample size for small to medium standardized effect sizes (0.2-0.6).

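### Hypotheses 1a (hospital stay) and 1b (one and three months) each concern a separate window, but the Aim 1 model describes time only as a linear or quadratic trend and names no estimate for either window

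*Combined protocol and SAP*

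**What the plan says.** Section 1 (Objectives, Aim 1) poses two hypotheses about different periods. Hypothesis 1a concerns less fatigue "during the course of HSCT hospitalization compared to those patients in the low light comparison condition". Hypothesis 1b states that "HSCT patients receiving sPI will report positive effects on CRF, depression, sleep, and circadian rhythm disruption at one month" and at three months. The opening summary draws the same line: assessments through the stay "to determine immediate impact of sPI), then repeat at one month and threemonths post-discharge follow-ups (to determine lasting effects". Section 5e (Methods) lists one or two baselines, then day of transplant, day +2, day +7, the third day of engraftment, and one and three months after discharge.

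Section 5g (Data Analysis) describes one family of mixed models for Aims 1 and 2. Its fixed effects are time, "Besides time (linear and possibly quadratic trends to allow for possible nonlinear trends", together with covariates and intervention group. It adds: "Each model will also include a random intercept. Post-hoc comparisons will be Tukey-adjusted". It does not say which comparisons, or at which visits.

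A time-by-treatment interaction appears in two places in the same section. One is the Aim 2 mediation analysis, which works by "introducing each individually into the equation which contains the time variable, the treatment main effect, and the time by treatment interaction". The other is the Power text, which covers both aims and discusses the interaction for depression in earlier data. It is not listed among the Aim 1 fixed effects.

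**The concern.** The light is given only in hospital, the visits are unequally spaced, and section 8 (Potential Benefits) says fatigue may come back once the light stops at discharge. A difference that is present during the stay and gone afterwards is therefore a pattern the protocol itself foresees. A straight line or a parabola over all visits fits that pattern poorly and moves part of the inpatient difference into follow-up.

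If the group main effect is the only treatment term, 1a and 1b receive the same number. If the interaction is included, it tests whether the arms differ in trend over all visits, which is neither hypothesis. Post-hoc comparisons read from the fitted trend inherit its misfit.

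The Power text makes this matter: "one of the goals of this project is to obtain estimates of the effect sizes that will eventuate from our proposed analyses", and these are to guide the size of a larger trial. A follow-up benefit produced by the shape of the model would mislead that planning.

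**Working it through.** **The plan's own figure.** Section 5g states power of 0.96-0.98 with 30 per group and alpha 0.05: "we calculated power for a repeated measures design with an autoregressive lag 1 structure and autocorrelations ranging from 0.40 to 0.60". No effect size, number of measurements or tested term is given, so it cannot be reproduced. As a single two-arm contrast it would imply d = (1.96 + 1.75)·√(2/30) = 0.96 to (1.96 + 2.05)·√(2/30) = 1.04. This does not show which Aim 1 term was powered.

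**Inputs.** From the documents: the visit list, 30 per arm, AR(1) correlation 0.4-0.6 and 71% expected retention. Assumed: FACIT at days -30, 0, 2, 7, 14, 44 and 104; unit SD; a true arm difference of 0.6 SD at the four inpatient visits and 0 elsewhere.

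**Method.** With balanced data, a random-intercept fit of the arm difference equals ordinary least squares of the true difference profile on 1, t (and t²).

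**Main effect only.** 0.6 × 4/7 = 0.34 SD over seven visits, or 0.6 × 4/6 = 0.40 SD over the six post-baseline visits. The same number serves both windows.

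**Linear in days, baseline as an outcome row.**
- Mean day = 141/7 = 20.14; mean difference = 0.343
- Sxx = 13901 − 141²/7 = 11060.9
- Sxy = 13.8 − 20.14 × 2.4 = −34.54; slope = −0.00312 per day
- Inpatient (mean day 5.75): 0.343 + 0.00312 × 14.39 = 0.39
- One month (day 44): 0.343 − 0.00312 × 23.86 = 0.27 (truth 0)

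**Linear in days, baseline as a covariate (six visits).**
- Mean day = 171/6 = 28.5; mean difference = 0.40
- Sxx = 13001 − 171²/6 = 8127.5
- Sxy = 13.8 − 28.5 × 2.4 = −54.6; slope = −0.00672 per day
- Inpatient: 0.40 + 0.00672 × 22.75 = 0.55
- One month: 0.40 − 0.00672 × 15.5 = 0.30 (truth 0)

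The same projection over all four forms (linear or quadratic, days or visit number) gives:

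| Baseline | Inpatient (truth 0.6) | One month (truth 0) |
|---|---|---|
| Outcome row | 0.36-0.54 | 0.26-0.45 |
| Covariate | 0.54-0.58 | 0.08-0.30 |

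AR(1) residuals do not remove the misfit: with baseline as a row, the one-month difference is still 0.21-0.44.

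**Only one inpatient FACIT (days -30, 14, 44, 104).**
- Linear in days, baseline as row: 0.15 − (11.4/9492) × 11 = 0.14 at one month
- Linear in days, baseline as covariate: 0.20 + (24/4200) × 10 = 0.26
- Quadratic, baseline as row: 0.28
- Quadratic, baseline as covariate: no bias, since three parameters fit three visits exactly

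**Precision and power of named contrasts.** For a contrast c, the variance is (2/n)·[c'Vc − (c'V₀)²], with V the AR(1) matrix by visit order and V₀ its baseline column. Power is two-sided 5% on 2n − 3 degrees of freedom. At n = 30 and correlation 0.4/0.6, standard errors are 0.168/0.180 for the four-visit inpatient mean and 0.145/0.166 for the six-visit main effect. Each follow-up contrast has about √(2/30) = 0.26 (√(2/21) = 0.31 at 71% retention).

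| True profile | Inpatient contrast | Main effect |
|---|---|---|
| Inpatient only (means 0.60 and 0.40) | 94%/91% | 77%/66% |
| Persisting: 0, 0, 0.3, 0.6, 0.6, 0.6, 0.6 (means 0.375 and 0.45) | 59%/54% | 86%/76% |

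**The case against.** The fairest defence is that the interaction probably belongs to Aim 1. One model family serves both aims, the Aim 2 text speaks of the interaction as part of an equation already in place, and the Power text uses it for depression, an Aim 1 outcome. A reader might infer that the interaction is confined to Aim 2; the Power text shows otherwise. What stands is that it is missing from the stated Aim 1 fixed effects, and that it would still test trend over all visits.

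A reader might also infer that the planned model cannot yield window estimates at all. It can, because fitted differences can be read off at any visit. The gap is that none is named and that they carry the misfit.

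The figures depend on open choices. The documents do not say that FACIT is given at every inpatient visit: section 5e has the Fatigue Line Scale replace it for daily inpatient use, and section 11 counts the stay as one time point. Strong dilution of the inpatient effect is not established either, because with baseline as a covariate it is small. The spurious one-month difference mostly remains, but vanishes for a quadratic with one inpatient visit and baseline as a covariate.

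Finally, bias is not the only criterion in a 60-patient feasibility study. Under fading or persisting profiles, a linear trend's one-month root-mean-square error is 0.15-0.21 SD, against a standard error of 0.26 SD for the visit-specific estimate. It is worse when the effect stops at discharge: 0.27-0.34 linear, up to 0.50 quadratic. Neither model is best throughout.

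**Conclusion.** The concern holds as a gap in specification that should be closed before analysis. Two window-specific hypotheses are posed, and no term, contrast or visit is assigned to either. If the effect is confined to the stay, the trend model would usually report a one-month benefit that does not exist. For a true 0.6 SD inpatient effect it is 0.08-0.45 SD under the assumed seven-visit schedule. With a single inpatient assessment it is 0.14-0.28 SD, apart from the one combination that has no bias. These sizes rest on assumed visit days, effect profile and FACIT schedule.

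The documents do not support a claim that the planned analysis lacks power, or that window contrasts would raise power in general. The point concerns outcomes measured at the scheduled visits in both windows; the daily Fatigue Line Scale is outside it. Feasibility status limits the severity but does not remove the point, because effect-size estimation is a declared goal.

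**What to change.** For outcomes measured at the scheduled visits, in section 5g:

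- Fit visit as categorical with a group-by-visit term and adjust for baseline. State which baseline is used when both baseline 1 and baseline 2 exist, for example the last one before admission.
- Name one inpatient contrast for 1a over the inpatient visits at which the outcome is actually measured, stating whether day 0 is included. Name a one-month and a three-month contrast for 1b. Report each with a confidence interval.
- State at which inpatient visits FACIT-Fatigue is given, and which comparisons the Tukey adjustment covers.
- Keep the polynomial model as supportive, stating its time coding and whether its interaction belongs to Aim 1.

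The cost is wording and a few more parameters; no new data are needed. The statistical price is lower power for the inpatient contrast than for the overall main effect when the benefit persists, and imprecise follow-up estimates, for which a trend would be more precise under some profiles. The order of testing between 1a and 1b is the sponsor's choice.

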- Eye Diseases which limit the ability of light to be processed (e.g., untreated cataracts, severe glaucoma, macular degeneration, blindness, pupil dilation problems or retina damage)
- Secondary cancer diagnosis within the last 5 years
- Severe sleep disorders (e.g., Narcolepsy)
- History of bipolar disorder or manic episodes (which is a contra-indication for light treatment)
- Severe psychological impairment (e.g., hospitalization for depressive episode in the past 12 months)
- Previous use of light therapy to alleviate fatigue or depressive symptoms

c) Number of Subjects

 Mount Sinai	Protocol Name:	Systematic Programmed Illumination of Hospital Rooms to Prevent/Reduce Cancer-Related Fatigue during Autologous Stem Cell Transplantation for Multiple Myeloma
	Principal Investigator:	[name]; [contact]
	Primary Contact Name/Contact Info:	[name], [contact], [contact]
	Date Revised:	8/15/2019
	Study Number:	IF# 2517160 HS# 15-00777 GCO#: 15-2009

For this feasibility study, we will recruit 60 participants drawn from the pool of upcoming HSCT admissions to treat MM at the MSH bone marrow transplant (BMT) clinic. Our previous research has demonstrated that at least 40% of this group either suffers from or will develop clinically significant fatigue related to cancer or its treatment.

d) Study Timelines

Total participation in this study is 16-18 weeks, and may vary by hospital admission, length of hospital stay, and expediency of returning study related materials.

Endpoints

The primary endpoints in the proposed study are: 1) Fatigue as measured by a simple Graphic Rating Scale, Multidimensional Fatigue FACIT Fatigue Scale, and The Pittsburgh Sleep Quality Index; 3) Depression as measured by the CES-D; 4) Quality of Life measured by the SF-36 scale; 5) Sleep/wake activity measured using an actigraph; and 7) Biological variables melatonin and inflammatory markers (i.e., IL-1ra, IL-6, MCP-1/CCL2, MIP-1a/CCL3, sTNFr1, sIL-6R, CRP) as obtained via urine and blood analysis.

The secondary endpoints include: 1) the amount of light received by the patient as measured by the Daysimeter; 2) treatment satisfaction using the FACIT-TS-G scale, and 3) Psychological moderators (e.g., emotions, symptom burden) that may affect for whom the treatment is effective.

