Data from any web-based assessment tools will be accessible to research study team using password protection and will only be identified by participant ID number. Paper files and printouts of assessment scores will be kept in a locked cabinet with access only by authorized project research staff. The use of email will be in accordance with MSH policy (i.e. secure email, obtaining consent from subject to send email, etc.).

Urine and blood samples will be marked only by study ID number and no other identifying information.

Data Analysis:

Descriptive statistics will be calculated both for the entire group and separately for each treatment group. T-tests and Fisher's exact tests will be used to assess group differences at baseline for possible confounders (i.e., demographic variables, clinical characteristics, and medications). Any variables showing differences between the two groups will be used as covariates in subsequent analyses. Since there is no known seasonality effect to measures of fatigue or to measures of sleep, which are our main outcome measures, seasonality will not be controlled in these analyses. For the primary outcome (Fatigue), the secondary outcomes (Depression, Sleep, Circadian Activity Rhythms, melatonin (exploratory), and Quality

	Protocol Name:	Systematic Programmed Illumination of Hospital Rooms to Prevent/Reduce Cancer-Related Fatigue during Autologous Stem Cell Transplantation for Multiple Myeloma
	Principal Investigator:	[name]; [contact]
	Primary Contact Name/Contact Info:	[name], [contact], [contact]
	Date Revised:	8/15/2019
	Study Number:	IF# 2517160 HS# 15-00777 GCO#: 15-2009

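### The Sidak clause for secondary outcomes does not identify one procedure; naming step-down Holm-Sidak and listing the family is a cheap improvement

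*Combined protocol and SAP*

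**What the plan says.** The multiplicity plan for the secondary outcomes is one clause of the Data Analysis text (section 5g): because there are several of them, "the p-values will be Sidak adjusted for correlated multiple comparisons". The text does not say whether this is single-step, step-down, based on an effective number of tests, or based on resampling. It gives no correlation estimate, no number of tests and no familywise level. The only alpha in that section belongs to the fatigue power statement: "With alpha equal to 0.05 and a sample size of 30 patients per group, power ranged between 0.96 and 0.98". Tukey adjustment of post-hoc comparisons is a separate step.

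The family is listed just before as "the secondary outcomes (Depression, Sleep, Circadian Activity Rhythms, melatonin (exploratory), and Quality" of Life. That is five domains, or four if melatonin stays exploratory. The Endpoints text under section 5d classifies outcomes differently. It begins "The primary endpoints in the proposed study are: 1) Fatigue as measured by a simple Graphic Rating Scale" and goes on to list depression, quality of life, sleep/wake activity and the biological variables as primary too.

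On scale, section 5c says "For this feasibility study, we will recruit 60 participants", and the power text says "one of the goals of this project is to obtain estimates of the effect sizes".

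**The concern.** The clause joins a method that ignores correlation to a statement that correlation is adjusted for. Two analysts could therefore compute different adjusted p-values from the same data and both claim to have followed the plan.

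The choice has consequences in both directions. An effective-number-of-tests version of Sidak does not hold the familywise error at its nominal level. Plain single-step Sidak does, but it gives up power that a step-down version recovers when several outcomes improve together. Hypothesis 1a predicts that pattern, with benefit on depression, sleep and circadian rhythm as well as fatigue.

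**Working it through.** **The plan's own figure.** The documents state no figure for the Sidak step. The stated power of 0.96–0.98 concerns fatigue at an unadjusted 0.05. It cannot be reproduced because the effect size, SD and number of time points are not given. The stated range, "autocorrelations ranging from 0.40 to 0.60", is correlation over time within one outcome, so it does not supply the correlation between outcomes needed here.

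**Inputs from the documents.** m = 4 or 5 (Data Analysis); 30 per group (power text); expected retention 71% (Preliminary research), so 0.71 × 30 = 21.3, or about 21 per arm.

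**Assumptions.** Familywise two-sided alpha 0.05; equal correlation r between outcomes, 0.3–0.7; effects of 0.5 and 0.7 SD.

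**Step 1: per-test levels.**
- Single-step Sidak: 1 − 0.95^(1/m), which is 0.0127 for m = 4 and 0.0102 for m = 5. There is no r in the formula.
- Effective-number version: 1 − 0.95^(1/m^(1−r)). For m = 5 and r = 0.5, m^(1−r) = √5 = 2.236, which gives 0.0227.
- Exact threshold from the joint distribution, m = 5 and r = 0.5: 0.0120.

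**Step 2: familywise error with all nulls true.** With c the two-sided critical value, φ and Φ the standard normal density and distribution function, and equicorrelated normal test statistics, the error is

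1 − ∫ φ(z) [Φ((c − √r z)/√(1−r)) − Φ((−c − √r z)/√(1−r))]^m dz.

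| r | Single-step Sidak, m = 5 | m^(1−r) version, m = 5 | m^(1−r) version, m = 4 |
|---|---|---|---|
| 0.3 | 4.75% | 7.5% | 7.1% |
| 0.5 | 4.3% | 9.0% | 8.4% |
| 0.7 | 3.5% | 9.8% | 9.0% |

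For reference, five independent unadjusted tests give 1 − 0.95^5 = 22.6%. In simulation at m = 5 and r = 0.5, step-down min-P using the correlation gives 5.0%. Holm-Sidak gives the same 4.3% as single-step, because its first threshold is the same. A step-down form of the m^(1−r) version still gives 9.0%.

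**Step 3: power, single-step against Holm-Sidak.** Simulated two-sample t-tests, m = 5, r = 0.5, 30 per arm. Average power is taken over the outcomes with a real effect.

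| True effects | Single-step | Holm-Sidak |
|---|---|---|
| All five, 0.7 SD | about 52% | about 62% |
| All five, 0.5 SD | 25% | 30% |
| Two, 0.7 SD | 52.4% | 54.0% |
| One, 0.7 SD | 52.9% | 53.0% |

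With all five at 0.7 SD, power to find at least one is 85.7% under both methods. At 21 per arm, average power is about 34% against 42%. A second calculation with z-tests gives 56% against 65% on average, and 21% against 44% for finding all five. There step-down min-P with known correlation reaches 67%, so Holm-Sidak recovers most of the available gain.

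**The case against.** A reader might infer that the plan must either waste power or exceed 5% error. The documents do not support that. The m^(1−r) formula appears nowhere in them. The clause could mean that Sidak was chosen because it stays valid for correlated outcomes, or it could mean a step-down or joint-distribution method. Inflation is a risk of one reading and not a demonstrated fault. This stands.

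A reader might also infer that going step-down cures both problems. It does not. Holm-Sidak ignores correlation too, so the conservatism at the first step remains. The inflation goes away only because the m^(1−r) formula is dropped, which plain Sidak would also do. This stands as well.

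The ten-point gain is a favourable case, since all five outcomes must improve by 0.7 SD. The only standardized range in the documents is 0.2–0.6, quoted for pilot sizing, and at 0.3 SD the gain is about one point (8% to 9%). The planned tests are covariate-adjusted mixed models, not t-tests, so the percentages compare methods and do not forecast this trial's power. Finally, the choice among valid familywise procedures for secondary outcomes matters less in a feasibility study.

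These points limit the size of the concern. They do not settle which procedure the clause means, and they leave single-step Sidak dominated on power by its step-down form.

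**Conclusion.** The point holds as a cheap improvement with low stakes. The clause is ambiguous. Under the m^(1−r) reading, familywise error would be about 7–10% for four or five outcomes at correlations of 0.3–0.7. Under the single-step reading, error is controlled but Holm-Sidak rejects whenever single-step does, and sometimes more, while staying at or below 5% in every case run. The average-power gain runs from essentially nothing (one real effect) to about ten points (five real effects of 0.7 SD). The correlations, effect sizes, equicorrelation and familywise 0.05 are assumptions.

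The documents do not support saying that the plan's error control is false, and they do not fix m at five. Melatonin is marked exploratory, and the Endpoints text calls several of these outcomes primary.

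**What to change.** Replace the clause with wording such as: *the secondary outcomes will be tested with the step-down Holm-Sidak procedure at familywise two-sided alpha 0.05*. Delete the words about correlated multiple comparisons. If the intention really is to use the correlation, name a joint-distribution method such as min-P instead.

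First reconcile the Endpoints text with the Data Analysis text on which outcomes are primary. Then list the family with one measure per domain. This is needed because Hypothesis 1a gives two depression scales and several sleep measures, so a domain is not yet a single test. Set the thresholds, in order of increasing p-value, as 1 − 0.95^(1/k) for k = m down to 1:
- m = 4 (melatonin kept exploratory): 0.0127, 0.0170, 0.0253, 0.05.
- m = 5: the same sequence preceded by 0.0102.

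The cost is a wording change with no new data or patients, best made before unblinded analysis. The one downside is that simultaneous confidence intervals are less direct than with single-step Sidak.

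### Aim 2 opens by requiring a significant treatment effect on fatigue and does not say whether the mediation bootstrap still runs without one; if the step binds, it can lose more than half of detectable indirect effects when the total effect is modest

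*Combined protocol and SAP*

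**What the plan says.** The Aim 2 text is in the Data Analysis part of section 5g. It proceeds in this order.

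- Opening step: "we will establish that the treatment is a significant predictor of the primary outcome (CRF) as well as the hypothesized mediators".
- Next, each mediator is added on its own to the fatigue model that holds time, treatment and their interaction. A filter follows: "Each mediator which is a significant predictor of CRF in this equation will then be combined with any other significant mediating predictor of CRF".
- The team predicts that adding a significant mediator will make the time-by-treatment term less significant.
- The text then ranks the tests: "the more important test of the mediating role by any variable will depend on the statistical significance of the indirect path". The method for this is that "1000 bootstrap samples will be employed to determine the significance of each indirect path".

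No sentence says whether the bootstrap is run if the opening step fails, or for a mediator left out of the combined equation. Section 1 words Aim 2 as exploratory. The Power paragraph gives no figure for Aim 2 and says of the effect sizes: "Although unknown at the moment, these effect sizes can guide decisions regarding sample sizes for a larger scale grant".

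**The concern.** An indirect effect is the product of two paths, and it can be real and detectable when the overall treatment effect on the outcome is not significant. In a small trial with no direct effect, the overall effect is often the hardest of these quantities to detect, because it is the product of the two paths tested against the full outcome variance. Requiring it first can close the mediation analysis for reasons unrelated to the mechanism.

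This matters because the study is meant to supply effect estimates for a larger trial. If indirect effects are reported only after significant first steps, the mechanism estimates may be missing where they are most needed. If the step is not meant to bind, the present wording leaves that decision until after the results are seen.

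**Working it through.** **1. The plan's own figure.** The only power statement that bears on the opening step concerns fatigue in Aim 1: "With alpha equal to 0.05 and a sample size of 30 patients per group, power ranged between 0.96 and 0.98", for "a repeated measures design with an autoregressive lag 1 structure and autocorrelations ranging from 0.40 to 0.60". It cannot be reproduced, because no mean difference, SD or number of repeated measures is given. It can be inverted to a standardised effect for a single two-arm contrast (two-sided 0.05 assumed, since sidedness is not stated):

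d = (1.960 + z_power) × √(2/30), with √(2/30) = 0.2582

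- power 0.96: (1.960 + 1.751) × 0.2582 = 0.96 SD
- power 0.98: (1.960 + 2.054) × 0.2582 = 1.04 SD

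**2. Sample size.** The opening summary states: "A sample of 60 patients scheduled for HSCT in the treatment of MM will be recruited". Section 2 expects 71% retention: 60 × 0.71 = 42.6, taken as 42 (21 per arm).

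**3. Model (assumed).** Treatment T is 0 or 1, allocated 1:1. Mediator M = a·T + e₁. Fatigue Y = b·M + c′·T + √(1 − b²)·e₂. Both errors have SD 1, so the within-arm SD of Y is 1 and the total effect is a·b + c′ in SD units. Each scenario has 1000 trials with 1000 bootstrap resamples and a 95% percentile interval for a·b. Monte Carlo error is about 1.6 points. The path sizes are assumptions, because the documents give none.

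**4. Results.** Power of the bootstrap alone, then of the bootstrap when treatment on fatigue, treatment on mediator and mediator on fatigue must each also reach p < 0.05. Share lost = 1 − (with tests ÷ alone).

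| a | b | c′ | total | N = 60, % | lost | N = 42, % | lost |
|---|---|---|---|---|---|---|---|
| 0.5 | 0.3 | 0 | 0.15 | 30.9 → 3.5 | 89% | 16.6 → 1.1 | 93% |
| 0.5 | 0.5 | 0 | 0.25 | 50.6 → 13.1 | 74% | 34.3 → 8.5 | 75% |
| 0.8 | 0.3 | 0 | 0.24 | 57.5 → 8.3 | 86% | 34.5 → 3.4 | 90% |
| 0.8 | 0.5 | 0 | 0.40 | 85.9 → 32.3 | 62% | 66.9 → 20.4 | 70% |
| 1.0 | 0.5 | 0 | 0.50 | 94.9 → 45.9 | 52% | 84.7 → 29.2 | 66% |
| 0.8 | 0.5 | −0.2 | 0.20 | 84.8 → 10.9 | 87% | 70.0 → 6.3 | 91% |
| 0.5 | 0.5 | 0.25 | 0.50 | 49.4 → 31.6 | 36% | 35.9 → 17.4 | 52% |
| 0.8 | 0.5 | 0.40 | 0.80 | 84.3 → 74.5 | 12% | 67.7 → 51.3 | 24% |
| 0.5 | 0.5 | 0.71 | 0.96 | 51.8 → 47.3 | 9% | 35.1 → 30.3 | 14% |
| 0.8 | 0.5 | 0.56 | 0.96 | 86.7 → 83.1 | 4% | 69.2 → 59.6 | 14% |
| 1.0 | 0.5 | 0.46 | 0.96 | 97.2 → 91.9 | 5% | 82.0 → 70.6 | 14% |
| 0.8 | 0.3 | 0.72 | 0.96 | 54.2 → 48.7 | 10% | 35.6 → 29.0 | 19% |

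For a = 0.7, b = 0.5, c′ = 0 (total 0.7 × 0.5 = 0.35), repeated runs gave 73% to 74% alone and 18% to 21% with the tests at N = 60, and 48% to 52% against 10% to 12% at N = 42.

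**5. Which test costs most.** For a = 0.8, b = 0.5, c′ = 0 at N = 60, treatment on fatigue is significant in 35% of trials. The normal approximation agrees: 0.40/0.2582 − 1.960 = −0.41, or about 34%. Adding that test alone takes bootstrap power from 86% to 33%. The treatment-to-mediator test alone takes it to 84%, and the mediator-to-fatigue test alone to 85%.

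**6. Sidak.** Section 5g applies a Sidak adjustment to the secondary outcomes, and several of these are also mediators. If it covered the treatment-to-mediator tests over the five listed outcomes, the per-test level would be 1 − 0.95^(1/5) = 0.0102. At N = 60 the loss would then be 53% to 94% with no direct effect and 13% to 55% at a total effect of 0.96 SD.

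**The case against.** The strongest reply is that no binding gate is written. The text has no stop rule, ranks the indirect path above the other tests, and promises a bootstrap for each such path. The one explicit filter decides which mediators enter the combined equation, not which are bootstrapped. This stands: the documents leave the point open. A reader might infer that Aim 2 would usually end with no mediator tested, and the text does not establish that.

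The second reply is that the size depends on the assumed effects. A reader might take from the upper rows of the table that the plan discards most true indirect effects at N = 60. That does not follow. At the total effect implied by the stated Aim 1 power, the loss is 4% to 10%. That benign case has limits of its own. The Power paragraph says that no past research is directly relevant, and its 0.96 to 0.98 comes from breast cancer chemotherapy. It also cites a pilot-sizing result for standardised effects of 0.2 to 0.6, where a single contrast with 30 per arm has about 12% to 63% power. A total of 0.96 SD carried wholly by one mediator with b = 0.5 would need a = 0.96/0.5 = 1.92 SD. Neither end of the range can be taken as settled.

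Third, the plan uses repeated-measures mixed models, so a single-contrast simulation does not estimate this plan's power. More measurements would raise power for all the tests. The percentages illustrate the mechanism and its range.

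Three further inferences go too far. The filter on mediators is not a main cause of lost power (step 5). The drop in significance of the time-by-treatment term is offered as a prediction ranked below the indirect path, not as the decision rule. That the combined equation overstates the retained mediators' effects is plausible, but no calculation here supports it.

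**Conclusion.** The point holds as a conditional one. The plan makes significance of treatment on fatigue and on the mediators the first step of Aim 2 and does not say whether the bootstrap depends on it. If it does, and if the indirect path carries the whole effect or the direct effect opposes it, more than half of bootstrap detections are lost at N = 60, and nearly all of that loss comes from the total-effect test. If the total effect is large, little is lost at full enrolment and 14% to 19% at 42 retained. The individual path tests add little unless they are Sidak-adjusted.

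These sizes rest on assumed paths, a single mediator, one post-baseline contrast and two-sided 0.05. Aim 2 is exploratory, so no confirmatory claim is at risk. The change is still worth making: the bootstrap is already planned, and a precondition works against the stated purpose of obtaining effect estimates.

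**What to change.** In the Aim 2 paragraph of section 5g:

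- Delete significance of the total effect, and of the individual paths, as a precondition for the mediation analysis.
- State that, for every mediator in Hypotheses 2a to 2d, the indirect effect will be reported with a 95% bootstrap interval whatever the total effect, resampling patients so that each patient's repeated measures stay together.
- Label all these results exploratory.
- State that a change in significance of the time-by-treatment term will not be used as evidence of mediation.

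A joint model containing all mediator domains is optional and not part of this fix. With 42 to 60 patients, seven named inflammatory markers, urine at two timepoints and blood at four, it has costs of its own.

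The cost is SAP wording only; data collection does not change. The downside is small: more exploratory indirect effects will be reported, so the multiplicity should be acknowledged alongside them.
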